3.1 Main objective

The main objective of this study is to compare the prevalence of global undernutrition based on the diagnostic criteria recommended by the French National Authority for Health with that based on the diagnostic criteria recommended by the Global Leadership Initiative on Malnutrition , in patients hospitalised in short-stay and follow-up care and rehabilitation in diabetes-obesity, pneumology, oncology and gastro-nutrition.

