9.1.2 Sampling of the population

A potential of 94 patients per month eligible for this study are admitted in the short stay and follow-up care and rehabilitation of diabetology-obesity, pneumology, oncology and gastro-nutrition. We anticipate a maximum inclusion of 13 patients per month for logistical reasons. In order to obtain a representative sample of this patient population in the study, we will sample the patient population on admission , if they meet the eligibility criteria and before the patient is informed and consents are obtained. The patient will be randomly assigned to either the eligible or the ineligible group of the study. Patients in the ineligible group will therefore not be included in the study, but the number of such patients will be collected.

Patients will be sampled via a centralised randomisation system available via the internet, according to a pre-determined randomisation list. The randomisation list will be scheduled in advance by the study statistician. The sampling will be stratified on the care service, and unbalanced using random blocks in order to obtain a number of eligible patients of 15 patients per month (in order to take into account possible refusals of participation). Only the hospital research coordinator will know the randomisation list.

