11.1 Calculation of the number of subjects needed

According to PMSI data, the prevalence of undernutrition according to HAS recommendations was 34%. Taking into account the wider period of weight loss and the higher BMI threshold used by GLIM in its definition of undernutrition, we estimate a higher prevalence of undernutrition. In the absence of data in the literature, we estimate a prevalence of undernutrition according to the GLIM definition at 49%, a difference of at least 15%. We wish to highlight this discrepancy. With a risk $\alpha = 0.05$ and a power of 80%, it will be necessary to include 260 patients.

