11.2 General aspects

Descriptive statistics will be based on means (+/- standard deviation) or medians [interquartile range] depending on the distribution of quantitative variables. Qualitative variables will be described in terms of numbers and percentages. Univariate comparisons will use the usual statistical tests after checking the distribution of the variables (Chi2 or Fisher's test, t-test, anova or their non-parametric equivalents Wilcoxon and Kruskal-Wallis tests). Paired sample tests will be used if necessary.

The tests will be performed at the 5% significance level. The 95% confidence intervals will be provided for each estimate.

The calculations will be done using SPSS v21 IBM and R software (version 3.6.1, <http://www.R-project.org>).

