11.4.2 Comparison of morbidity and mortality

Morbidity and mortality will be compared between the HAS and GLIM groups, for moderate and severe undernutrition, by comparing the length of hospital stay, mortality and autonomy at discharge.

Length of stay in hospital

There is a relationship between the incidence of mortality and all length of stay variables. Length of stay will therefore be analysed using a competitive risk method, which takes into account the fact that patients who die are no longer eligible for length of stay analysis (25).

The estimator also provides the probability of in-hospital death, so that the probability of hospital discharge versus death at any time after inclusion in the study can be assessed simultaneously.

Mortality rate

The estimation of mortality rates will be carried out by the Kaplan and Meier method. The comparison of the 2 curves will be performed by a Logrank test. The mortality rates in the 2 groups will be estimated via the survival curves.

ADL

The ADL score will be compared between the 2 groups using the discrete numerical variable comparison tests described in the general aspects.

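### Stay, mortality and ADL are compared between the HAS and GLIM groups without using care service or type of stay, so any difference in ward mix would enter uncorrected

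*Combined protocol and SAP*

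**What the plan says.** Section 11.4.2 compares the HAS and GLIM groups, for moderate and severe undernutrition, "by comparing the length of hospital stay, mortality and autonomy at discharge". Stay is analysed by a competing-risk method with death as the competing event. Mortality is analysed by Kaplan-Meier curves and a logrank test, and ADL by the tests of section 11.2. That section states: "Univariate comparisons will use the usual statistical tests after checking the distribution of the variables". It allows paired tests if needed, promises a 95% confidence interval for each estimate, and adds: "The tests will be performed at the 5% significance level". Section 11 names no stratum, covariate or multivariable model for any outcome.

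The population is mixed by design. The main objective (3.1) concerns prevalence "in patients hospitalised in short-stay and follow-up care and rehabilitation in diabetes-obesity, pneumology, oncology and gastro-nutrition", and the inclusion criteria (5.1) admit the same pooled population. On sampling, section 9.1.2 says: "The sampling will be stratified on the care service". Section 9.2 collects hospital service, reason for admission, age and sex at inclusion. Type of stay (short stay or follow-up/rehabilitation) is not listed as a separate item in 9.2 or in the table in 9.4.

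**The concern.** Length of stay, risk of death and autonomy at discharge can be expected to depend on whether the patient is in a short-stay or a rehabilitation bed, and on the specialty. The two definitions use different BMI and weight-loss limits and different muscle measures (1.5, 10.1), so they need not pick up patients in the same proportions from each ward. If they do not, an unadjusted comparison mixes the prognosis attached to a definition with the prognosis attached to a ward.

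Stratified sampling does not prevent this. It makes the sample resemble admissions, but it does not make the HAS-positive group resemble the GLIM-positive group. What is at stake is the secondary objective on morbidity and mortality, which section 2 presents as a question about the prognostic character of undernutrition under each definition.

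**Working it through.** **1. The plan's own figures.** Section 11.1 gives 34% (HAS), 49% (GLIM), alpha 0.05 and "a power of 80%, it will be necessary to include 260 patients". For two independent groups, tested one-sided:

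- n per group = [1.645·√(2·0.415·0.585) + 0.842·√(0.34·0.66 + 0.49·0.51)]² / 0.15² = 133, total 266. The unpooled form gives 131, total 262.
- The two-sided total is 338.

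So 260 is approximately reproduced only as a one-sided total for independent groups. It was set for the primary endpoint and does not bear on the outcome comparisons. It is used here only for group sizes: 0.34 × 260 ≈ 88 HAS-positive and 0.49 × 260 ≈ 127 GLIM-positive.

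**2. Structure.** Both definitions are applied to every patient, which is why 11.3 uses McNemar. The groups overlap, so their ward mix can differ only through patients positive on one definition alone.

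**3. Nested case (assumption: every HAS-positive patient is GLIM-positive).** GLIM-only patients are (49 − 34)/49 = 15/49 = 30.6% of GLIM-positives. With stay depending only on type of stay:

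spurious difference (GLIM − HAS) = 0.306 × (rehabilitation share in GLIM-only − share in HAS) × (rehabilitation − short-stay mean stay)

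The documents give one overall mean stay, about 30 days (6.3). Shares and gaps below are assumptions.

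| Rehabilitation share, HAS vs GLIM-only | Mix difference | Absolute difference in mean stay |
|---|---|---|
| equal | 0 | 0 days |
| 50% vs 30% | 6.1 points | 0.6 / 1.2 / 1.8 days (gap 10 / 20 / 30) |
| 70% vs 20% | 15.3 points | 1.5 / 3.1 / 4.6 days (same gaps) |
| 100% vs 0% | 30.6 points | 9.8 days (gap 32) |

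The 32-day gap is 40 versus 8 days. With 69% in rehabilitation it fits the overall mean: 0.69 × 40 + 0.31 × 8 = 30.1. If GLIM-only patients are more often in rehabilitation, the sign reverses.

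**4. Not nested.** Assume 24% of patients are positive on both, so 10% are HAS-only and 25% GLIM-only. Let rehabilitation shares be 50% (both), 60% (HAS-only) and 30% (GLIM-only).

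- HAS: (0.24 × 0.50 + 0.10 × 0.60)/0.34 = 52.9%
- GLIM: (0.24 × 0.50 + 0.25 × 0.30)/0.49 = 39.8%
- Difference 13.1 points, or 3.9 days at a 30-day gap.

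**5. Within severity classes.** The 30.6% ceiling need not apply. By section 10.1, HAS-moderate BMI is 17 to 18.5, while BMI below 18.5 is already GLIM-severe. If the compared groups shared no patients, 50% versus 30% would give 0.20 × 10 / 20 / 30 = 2 / 4 / 6 days.

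**6. Simulation.** Settings: 260 patients, 4,000 runs, gamma-distributed stays with means of 10 and 40 days by type only, t-test on log stay, no deaths, groups treated as independent. Rates are the share of runs significant at 5%.

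| Scenario | Unadjusted | Adjusted for type of stay |
|---|---|---|
| Nested, equal mix | 0.0% | 0.0% |
| Nested, 50% vs 30% | 0.2% | 0.0% |
| Nested, 60% vs 30% | 0.6% | 0.0% |
| Nested, 70% vs 20% | 12.6% | 0.0% |
| Step 4, equal mix | 0.2% | 0.3% |
| Step 4, mixes as given | 12.8% | 0.2% |
| Step 4, HAS-only share 70% | 24.6% | 0.4% |
| HAS-only vs GLIM-only, same last two mixes | 40.7%; 62.8% | 4.7%; 5.4% |

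Adjustment removes the spurious signal. With equal mix, however, a nominal 5% test rejects in 0.0% to 0.2% of runs because the same patients sit in both groups. That fault is separate, and adjustment does not cure it.

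**The case against.** The strongest case against has four parts.

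- **The target is open.** If the question is how patients labelled by each definition fare, a different ward mix is part of what the definition does, and adjusting removes something real. This stands in part. Section 2 points towards prognostic value, but 11.4.2 does not say so. The target should be stated, and the unadjusted figures kept.
- **No mix difference is shown.** A reader might infer that the planned comparison is biased by several days. The documents do not support that: they give no stay by type of unit, no service mix and nothing on where patients positive on one definition alone are treated. Zero is within the range. With nested groups and a moderate mix difference, the planned kind of test would rarely flag it. That low rate is limited comfort, because the test is far too conservative with shared patients and the shifted estimate would still be reported with its interval.
- **Stratifying is not enough.** A reader might also infer that stratifying by service alone repairs 11.4.2. It does not: under nesting, about 88 of 260 patients would still be counted in both groups by tests that assume independence.
- **The data are thin.** Four specialties by two types of stay gives up to eight strata. The 0.15 × 260 = 39 GLIM-only patients average about five per stratum, before any split by severity. Reason for admission is uncategorised and overlaps the disease-based aetiological criterion. This stands and limits what should be asked.

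On the other side, nesting is itself only an assumption. The HAS list of muscle measures includes grip strength and gait speed, whereas GLIM treats grip as complementary (1.5), so HAS-only patients are possible and the dilution could be weaker than in step 3.

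**Conclusion.** The point holds in a limited form. No analysis of stay, mortality or ADL uses care service or type of stay, and nothing else in the plan would keep a ward-mix difference out of the HAS-GLIM comparison. Whether such a difference will occur, and how large it would be, is not known from the documents.

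Under nesting, the illustrative effect on mean stay runs from 0 days, through 0.6 to 1.8 days for a moderate difference, to 9.8 days at an extreme that no one should expect, in either direction. It could be larger for the same mix if the groups are not nested or are compared within severity classes. No figure can be given for mortality or ADL. These are secondary comparisons and the primary prevalence analysis is unaffected. The change is worth making because it is cheap and serves the plan's own question. Confidence is moderate.

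**What to change.** In section 11.4.2:

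1. State that the target is the prognostic value of each definition.
2. Compare outcomes in a way that respects shared patients. Either use four categories (positive on both, HAS only, GLIM only, neither), or fit a whole-cohort model for each definition and compare the two by paired bootstrap.
3. Include care service and type of stay as strata or covariates. Add age and sex for length of stay and ADL. For death, where events may be few, stratify only.
4. Set in advance a rule for merging sparse strata, and do not require adjustment for the uncategorised reason for admission.
5. Keep the unadjusted figures as descriptive.

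In section 9.2, list type of stay as a data item, or state how it is derived from the service.

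The cost is revised analysis wording, slightly more analysis work, some loss of precision from small strata, and at most one administrative field.

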4.2 Secondary outcomes

The secondary outcomes will be :

- Prevalences of severe undernutrition according to the HAS and GLIM diagnostic methods;
- Morbidity and mortality criteria related to moderate and severe undernutrition according to the HAS and GLIM diagnostic criteria :
 - Duration of hospital stay (days) ;
 - Mortality: proportion and date of occurrence of death among patients included during hospitalisation;
 - Autonomy at discharge: Activities Daily Living score (ADL, [Appendix 1](#)).
- Measures of muscle function :
 - Bioelectrical impedance measurement ;
 - Handgrip ;
 - Walking speed.

5 Eligibility criteria

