6.2 Research scheme

6.3 Provisional research timeline

The duration of recruitment will be 20 months with follow-up of patients during their entire hospital stay in the care unit, i.e. approximately 30 days (average length of stay), for a total estimated study duration of 21 months.

- Submission to PPC: November 2021
- Start of inclusions: February 2021
- Duration of the inclusion period: 20 months
- Duration of participation of each patient: 30 days
- End of inclusions: October 2023
- Total duration of the research: 21 months
- Conference papers: congresses of medical societies of oncology, surgery, pneumology, nutrition and gastroenterology
- Publication: February 2024

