9.3 End of research visit

The end-of-research visit will take place when the patient is discharged from hospital or dies.

The following data will be collected:

- Duration of hospital stay (in days) ;
- Vital status (death yes/no) ;
- Autonomy score (Katz ADL).

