10.3.2 Mortality

Number of deaths out of the total number of patients included. A special statistical treatment (**described in section 11.4**) will be performed on the mortality rate.

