15.6 Information note and express consent

In accordance with Article L.1122-1 of the Public Health Code, the information provided to the persons who are to be involved in the research is the subject of a written document submitted in advance to the personal protection committee. The ethical opinion of the CPP Ile de France 2 was sought.

The investigator at the centre offers the patient, or a relative if the patient is incapacitated, to participate in the study. The investigator informs the patient orally of the study procedures and gives him/her the information note. If the patient gives free, informed and express oral consent to participate in the protocol, the information given orally and in writing, as well as the collection of oral consent, will be recorded in the patient's medical record.

In the event that a relative of the patient has given consent, as soon as possible, the patient will be informed of the research and asked for oral consent for the possible continuation of the research.

Patients are free to participate or withdraw from the study at any time in accordance with Article 21 of the GDPR. Data collected until the patient withdraws consent will be used unless the patient expressly requests otherwise. The withdrawal of consent by the patient and the agreement to use or not the data previously collected will be traced in the patient's medical file.

When the research is completed, the person who has undergone the research may be informed of the overall results of the research in the manner specified in the information document.

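### In-hospital mortality is to be read from Kaplan-Meier curves although follow-up ends at discharge, so the rates will overstate in-hospital death and disagree with the competing-risk estimate planned in the same section

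*Combined protocol and SAP*

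**What the plan says.** The mortality endpoint in section 4.2 is "Mortality: proportion and date of occurrence of death among patients included during hospitalisation". Section 10.3.2 defines it as "Number of deaths out of the total number of patients included. A special statistical treatment", and refers to section 11.4 for that treatment.

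Follow-up covers the hospital stay only, about 30 days on average (section 6.3). Section 9.3 fixes its end: "The end-of-research visit will take place when the patient is discharged from hospital or dies". Vital status is collected at that visit and not afterwards.

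Section 11.4.2 then produces in-hospital mortality in two ways:

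- Under length of stay, it plans a competing-risk method and notes: "The estimator also provides the probability of in-hospital death, so that the probability of hospital discharge versus death at any time after inclusion" can be assessed together.
- Under mortality rate, it states: "The estimation of mortality rates will be carried out by the Kaplan and Meier method". The curves are compared by a log-rank test, and "The mortality rates in the 2 groups will be estimated via the survival curves".

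The section does not say how patients discharged alive enter the Kaplan-Meier analysis, at what day the curves are read, or which estimate is the reported one.

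**The concern.** Kaplan-Meier estimates the probability of an event when censored patients remain exposed to the same future risk as those still under observation. A patient who has gone home can no longer die in hospital. Censoring that patient at discharge lets the patients who remain stand in for someone whose risk of the event is now zero. The result describes a hypothetical ward from which nobody is discharged, not the probability of dying during the stay. Withdrawals of consent (section 15.6) are ordinary censoring and do not raise this problem.

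Two things are at stake. First, the report could carry different figures for the same quantity, with the biased one attached to the mortality endpoint. Second, 1-KM follows the death hazard per day in hospital. Two groups with the same proportion dying but different stays would therefore show different mortality rates, and length of stay is itself a compared outcome. If stays do not differ, this second problem disappears.

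**Working it through.** The documents give no mortality figure to reproduce, so the check measures the gap between the two estimators.

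**Inputs**
- Mean stay of 30 days: section 6.3.
- Follow-up ending at discharge or death: section 9.3.
- 260 patients, with prevalences of 34% (HAS) and 49% (GLIM): section 11.1. This gives 0.34 × 260 = 88 and 0.49 × 260 = 127 patients.
- Proportion p dying in hospital: not given. Assumed 5-15%, with 8% for illustration.
- Patients discharged alive censored at discharge: assumed, since no rule is written.

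**Constant hazards.** The total exit hazard is 1/30 per day and the death hazard is p/30.
- 1-KM(t) = 1 − exp(−p·t/30)
- Cumulative incidence CIF(t) = p·(1 − exp(−t/30))

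For p = 0.08 and t = 60, 1-KM = 1 − exp(−0.16) = 14.8% and CIF = 0.08 × (1 − exp(−2)) = 6.9%, a ratio of 2.14. Each cell below shows 1-KM v CIF, with the ratio:

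| Assumed p | Day 30 | Day 60 | Day 90 |
|---|---|---|---|
| 5% | 4.9 v 3.2% (1.54) | 9.5 v 4.3% (2.20) | 13.9 v 4.8% (2.93) |
| 8% | 7.7 v 5.1% (1.52) | 14.8 v 6.9% (2.14) | 21.3 v 7.6% (2.81) |
| 15% | 13.9 v 9.5% (1.47) | 25.9 v 13.0% (2.00) | 36.2 v 14.3% (2.54) |

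**Simulation.** With 260 patients, p = 8% and 4000 runs, the means are 7.7 v 5.1%, 14.8 v 6.9% and 21.6 v 7.6%. In a second set (2000 runs per setting, p from 2% to 15%, several stay distributions and group sizes), 1-KM at the end of the curve was never below the CIF. For p = 5%, 260 patients and exponential stays, the curve ends on average at 26.9% for 1-KM and 5.0% for the CIF. Only the CIF ends at deaths over patients included, the definition in section 10.3.2.

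**Other stay distributions.** With gamma stays of mean 30 days and a constant death fraction, 1-KM = 1 − S(t)^p and CIF = p·(1 − S(t)), where S(t) is the proportion still in hospital. Over shapes 0.7 to 4 and p = 5-15%, the ratio is 1.4-1.6 at day 30, 1.9-3.1 at day 60 and 2.4-5.3 at day 90.

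**Patients still at risk.** Under constant hazards exp(−t/30) is 36.8%, 13.5% and 5.0% at days 30, 60 and 90. In groups of 88-127 that is about 32-47, 12-17 and 4-6 patients.

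**Between groups (illustration, day 60).** Here p = 8% in both groups and only the mean stay differs.
- 28 v 32 days: 1-KM 15.8 v 13.9% (1.8 points apart); CIF 7.1 v 6.8% (0.3 points).
- 27 v 33 days: 1-KM 16.3 v 13.5% (2.8 points); CIF 7.1 v 6.7% (0.4 points).

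Conversely, with the death hazard held at 0.05/30 per day and mean stays of 20, 30 and 40 days, day-60 1-KM is 9.5% each time, while the CIF is 3.2%, 4.3% and 5.2%.

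**The case against.** **The bias depends on an unwritten rule.** If discharged patients were kept as alive to a common horizon, 1-KM would equal the crude proportion, which fits section 10.3.2. Section 6.3 also lists 30 days as each patient's participation. But that section explains 30 days as the average stay, section 9.3 ends follow-up at discharge, and no fixed horizon is written for the mortality analysis. Censoring at discharge is the natural reading, and silence on the point needs correcting in any case.

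**Valid figures will exist anyway.** The competing-risk probability and the crude proportion are both planned, and the primary McNemar analysis and sample size are untouched. This stands and limits the severity. It does not help that the estimator named for mortality is the wrong one.

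**The size depends on the day chosen.** Day 30 is the only duration in the documents. There, at 8% mortality, the gap is 2.6 points, and 1-KM (6.5-8.2% over the gamma shapes) lies near the crude 8%. That closeness is coincidental: the probability of dying by day 30 is 5.1% under constant hazards. The top day-90 ratio of 5.3 does deserve discounting. It comes from gamma shape 4, where about 0.2% are still in hospital, less than one patient in groups of this size.

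**The between-group example ignores overlap.** HAS and GLIM classify the same patients. If every HAS case were also a GLIM case, group means of 28 v 32 days would require the GLIM-only patients to average about 41 or 19 days: (49 × 32 − 34 × 28)/15 = 41, or (49 × 28 − 34 × 32)/15 = 19. This stands. The example shows the mechanism and does not forecast a difference.

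**Conclusion.** The concern holds. As written, section 11.4.2 assigns to in-hospital mortality an estimator that does not estimate it, one paragraph after planning one that does. With discharged patients censored, the direction of the error does not depend on the death rate. Its size does: under constant hazards, a 30-day mean stay and 5-15% mortality, the overstatement is about 1.5-fold at day 30, 2.0- to 2.2-fold at day 60 and 2.5- to 2.9-fold at day 90, with few patients at risk by the later days.

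The conclusion rests on censoring at discharge, which is the default but is not stated. The error lies in the estimated rates. A log-rank test with the same censoring still compares cause-specific death hazards, though only between mutually exclusive groups. The endpoint is secondary, so this should be corrected but does not threaten the primary result.

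**What to change.** In section 11.4.2, replace the Kaplan-Meier mortality rates with the cumulative incidence of in-hospital death (Aalen-Johansen) at a stated day. Treat discharge alive as the competing event and censor withdrawals. Report with it the crude proportion of section 10.3.2 and its 95% confidence interval, and say which figure is the main one. If the log-rank test is kept, describe it as a comparison of cause-specific death hazards and not of mortality rates.

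The cost is wording in 11.4.2 only: the competing-risk analysis is already planned and no new data are needed. The overlap of the HAS and GLIM groups is a separate problem. Neither the log-rank nor Gray's test solves it, and redefining the compared groups would be a further change not costed here.
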